If AT-HOME PD study participants will be considered for any future follow up research their contact information will be obtained from the University of Rochester (UR) secure HIPAA compliant database based on original consent. If the subject declined contact in the original study, the subject will be allowed to contact the UR AHPD study team directly with an interest in study participation.

Considering the low participant burden of remote data collection, an inherent advantage of the outcome measures under investigation, we anticipate a modest dropout rate of ~15% from the tele-visit component over the two-year extension study. In addition, recruitment and retention will be motivated by multiple tested strategies ranging from reasonable reimbursement payments (to be paid in three installments following each tele-visit via check) to regular communication with participants.

Formative research through patient interviews indicates that long-term data collection in a remote setting will only be sustainable with a smartphone application that is specifically designed to meet the needs and interests of the participant population. Based on initial interviews, engagement strategies will focus on altruism, self-exploration, education, and community. These are implemented through the application using news feeds, infographics, participation dashboards, and notifications. Importantly, participants will be provided with the option to view the outcomes of their assessments in a manner that was highly effective at promoting engagement within mPower but was not feasible during the smartphone sub-study (Smart4SURE) of SURE-PD3.

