## 13. STATISTICAL ANALYSIS

Planned analyses are summarized here. Additional details will be included in a separate Statistical Analysis Plan (SAP). In the event of a conflict between the protocol and the SAP, the SAP will take precedence.

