We will compare TV vs. calibrated SP measures of disease progression generally, as predictors of future clinical events and changes in patient reported outcomes, and between specific subsets of participants expected to progress at different rates (Aim 2b) due to biology or treatment. After calibration, we will estimate the standard error for a treatment-group comparison from a two-arm trial using measure-specific variance components from a bivariate random-slopes linear mixed model for each pair of TV and SP measures and assuming an assessment schedule appropriate for each measure, e.g., annual for TV measures and quarterly for SP measures. Preferred measures would have smaller standard errors, and specifically, the ratio of squared standard errors provides an estimate of the relative sample size required. We will use the same approach to identify measures that are significantly more sensitive to biological

subgroups (e.g., among participants stratified by their rate of MDS-UPDRS progression over the first 2 years of in-clinic follow-up in the parent trials) or treatment-based subgroups (e.g., participants randomized to Isradipine or serum urate elevation). To compare TV assessments and SP measures with respect to their accuracy in predicting future clinical events and changes in patient reported outcomes, we will use the same 2:1 training: validation split and train separate models using TV and SP metrics collected over the first year of follow-up to predict clinical events and changes in PROs over the second year of follow-up. Clinical events will include dropping below 80% on the modified Schwab and England ADL and experiencing a fall. PROs of interest will include summary scores from the PDQ-8, EQ-5D, and PDAQ-15 and measures derived from the PD-PROP. Selection of the best training models will be based on 10-fold cross-validated accuracy for binary outcomes and residual sum of squares for continuous measures. Positive and negative predictive values of TV and SP-derived predictions will be estimated from the validation sample for binary outcomes and compared by logistic regression. For continuous outcomes, RSS estimates will be compared between TV and SP-derived predictions. As an exploratory analysis, additional models that combine TV and SP measures will be constructed and tested for accuracy relative to models derived from TV or SP measures alone.

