Completion rates of PROs collected during TVs vs. those collected online via FI will be compared by mixed effect logistic regression with participant-specific and participant x form random effects (Aim 2c). Concordance between PROs assessed during TVs vs. those obtained online via FI will be estimated using Lin's concordance correlation coefficient (Aim 2c).

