#### 13.4 Sample Size Determination

SA 1b. With a sample size of ~10 SURE-PD3 and ~50 SUPER-PD participants expected to complete at least one TV close in time to their in-person clinic visit, the study will have 80% power to conclude that the REACT-PD calibrated tele-visit estimates are sufficiently accurate ( $r_c > 0.8$  at  $\alpha = 0.05$ ) if the true concordance is at least 0.89.

SA 2a. With a 2:1 split of ~340 AT-HOME PD participants, yielding ~115 participants contributing to validation tests, the study will have 80% power to declare a given SP measure sufficiently accurate ( $r_c > 0.80$  at  $\alpha = 0.05$ ) if the true concordance is at least 0.87.

SA 2b. With approximately 80% of participants participating in the SP portion of the study, yielding ~340 participants contributing to the smartphone vs tele-visit comparison, the study would have an 80% probability of selecting the true preferred measure from a pair of TV or SP if the preferred measure had lower standard error by an effect size of at least 0.065.

SA 3. With a 2:1 split of ~240 participants, yielding ~80 in the validation sample and at least 25% experiencing at least an 8-point progression in MDS-UPDS parts 1-3 total score, the study would have 80% power to

declare a novel measure derived from passive SP monitoring to have a ROC AUC significantly greater than 0.80 if the true AUC were at least 0.95.

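### The TV-versus-SP comparison of predictive values uses paired data, but the plan names only logistic regression; if records are treated as independent, the test is conservative and loses power.

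*Combined protocol and SAP*

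**What the plan says.** Section 13.2, Aim 2b, sets up the prediction comparison this way: "we will use the same 2:1 training: validation split and train separate models using TV and SP metrics". Metrics from the first year predict events in the second. The binary outcomes are a fall and a drop below 80% on the modified Schwab and England scale. On the comparison itself the plan has one sentence: "Positive and negative predictive values of TV and SP-derived predictions will be estimated from the validation sample for binary outcomes and compared by logistic regression".

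Two neighbouring analyses do state how within-participant dependence is modelled. For progression, the same section uses a "bivariate random-slopes linear mixed model for each pair of TV and SP measures". For Aim 2c, completion rates "will be compared by mixed effect logistic regression with participant-specific and participant x form random effects".

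Section 13.4 (SA 2a) gives the size of the validation subset: "yielding ~115 participants contributing to validation tests". It gives no power figure for the predictive-value comparison. Section 5.1 adds: "we anticipate a modest dropout rate of ~15% from the tele-visit component over the two-year extension study". The opening of Section 13 calls its content a summary, leaves further detail to a separate SAP and gives that SAP precedence. No method for the pairing appears in the text available.

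**The concern.** Both models are scored on the same validation participants against one outcome per participant. Someone classed as positive by both models enters the TV and the SP positive predictive value (PPV) with the same result. Someone classed as negative by both does the same for the negative predictive value (NPV). The two estimates are therefore positively correlated. A logistic regression on stacked records with its default variance ignores that and makes the standard error of the difference too large.

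Section 2.1 makes the platforms' ability to predict clinical events an objective (Aim 2b(i)). With about 115 validation participants, an overstated standard error could lead to a report of no difference when one platform predicts better, with intervals that are too wide.

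**Working it through.** **Plan figures.** 340/3 = 113, in line with about 115. The SA 2a power statement reproduces by Fisher z with a one-sided 0.05 test: (atanh 0.87 − atanh 0.80) × √112 − 1.645 = 0.2345 × 10.58 − 1.645 = 0.837, power 0.80. With a two-sided test it would be 0.70. So 115 is a sound input. After 15% dropout, 115 × 0.85 ≈ 98.

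**Assumptions.** The plan gives no event rate, accuracy, TV–SP agreement or alpha for this comparison. I take event rates of 15–40%, score correlation within outcome group of 0–0.9, two-sided 0.05, and one prediction per model per participant.

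**Direction.** For a participant positive on both models with outcome D, the covariance term is (D − PPV_TV)(D − PPV_SP). This equals (1 − PPV_TV)(1 − PPV_SP) if D = 1 and PPV_TV × PPV_SP if D = 0. Neither is negative, and the same holds for NPV. Ignoring the term can only overstate the variance of the difference.

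**Size by hand.** Let π be the proportion positive and q1, q0 the proportions positive on both models with D = 1 and D = 0. With equal accuracy, the fraction of the independent-records variance (log-odds scale) that the pairing removes is

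s = [q1(1 − PPV)² + q0 PPV²] / [π PPV(1 − PPV)], and model variance / true variance = 1/(1 − s).

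Take sensitivity = specificity = 0.70 and 25% events:

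- π = 0.25 × 0.70 + 0.75 × 0.30 = 0.40 and PPV = 0.175/0.40 = 0.4375.
- Correlation 0: q1 = 0.25 × 0.49 = 0.1225 and q0 = 0.75 × 0.09 = 0.0675. Then s = (0.1225 × 0.3164 + 0.0675 × 0.1914)/0.0984 = 0.525, ratio 2.1.
- Correlation 0.5: the both-positive probabilities are 0.557 (D = 1) and 0.157 (D = 0). Then s = 0.676, ratio 3.1.
- NPV = 0.525/0.60 = 0.875. The matching ratios are 1.5 (correlation 0) and 2.3 (correlation 0.5).

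So the variance is already overstated when the scores are uncorrelated within outcome group, because the outcome is shared.

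**Simulation, equal accuracy.** Correlated binormal scores, n = 115, 4,000–20,000 replicates per cell. An independent-records Wald test is compared with a participant-clustered one. In the same case at correlation 0.5, the variance ratio is 2.97 (PPV) and 2.02 (NPV). Rejection at nominal 5% is 0.06% unclustered against 4.8% clustered for PPV, and 0.2% against 4.0% for NPV. As a check, 1.96 × √2.97 = 3.38, and a standard normal exceeds that in absolute value 0.07% of the time.

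Over all equal-accuracy cells (0.70 or 0.80):

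- The ratio is 1.2–4.4 for correlations 0–0.7, and reaches 7.4 at 0.9.
- Unclustered rejection is 0.0–1.5%.
- Clustered rejection is 3.9–5.0% for PPV and 1.2–4.7% for NPV, lowest when events are few.

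**Simulation, unequal accuracy (power).**

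| Accuracy of the two models | Events | Correlation | n | Measure | Unclustered | Clustered |
|---|---|---|---|---|---|---|
| 0.60 vs 0.85 | 25% | 0 | 115 | PPV | 93% | 99% |
| 0.60 vs 0.80 | 40% | 0 | 115 | PPV | 73% | 90% |
| 0.65 vs 0.80 | 25% | 0.5 | 115 | PPV | 37% | 86% |
| 0.65 vs 0.80 | 25% | 0.5 | 115 | NPV | 17% | 51% |
| 0.65 vs 0.80 | 25% | 0.5 | 98 | PPV | 28% | 79% |
| 0.70 vs 0.80 | 15% | 0.7 | 115 | PPV | 4% | 63% |
| 0.70 vs 0.80 | 15% | 0.7 | 115 | NPV | 1% | 18% |
| 0.70 vs 0.75 | 25% | 0.5 | 115 | PPV | 1% | 19% |
| 0.70 vs 0.75 | 25% | 0.5 | 115 | NPV | 1% | 10% |

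**Cross-checks.** A separately coded simulation (20,000 replicates per scenario, events 20–40%, correlation 0–0.8, n = 98 or 115) gave unclustered type I error of 0.000–0.013. At n = 1,000 it was still 0.000–0.018, so this is not a small-sample effect. On one simulated data set, standard software gave the same log-odds PPV difference (−0.86) from both fits, with SE 0.479 for independent records and 0.331 clustered and robust.

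**The case against.** The strongest reply is that this argues from silence. Logistic regression names a model family, not a variance estimator, and a clustered or mixed fit would also satisfy the sentence. Section 13 describes itself as a summary and defers to an SAP that is not available here. The nearby mixed models show a team that does handle dependence, which makes the naive analysis less likely. The error is in the conservative direction, and no power claim or decision rule rests on this test.

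Much of that stands. That an unclustered model is intended is an inference, and the harm arises only if records are stacked and the default standard error is used. But where dependence is handled in Section 13.2 it is named, and here it is not. Section 13.2 also carries the title of the analysis plan.

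Two further points stand as limits. First, the correct test is still weak for small gaps or few events, as the 0.70 versus 0.75 rows show, so a missed difference remains possible after the change. Second, n = 115 is generous. About 98 is more realistic after dropout, and people already below 80% on Schwab and England cannot drop below it. Participants with TV data only would shrink the effect without reversing it. Repeated predictions per model would add clustering in the opposite direction, but the text reads as one prediction per model.

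**Conclusion.** The concern holds in its conditional form. The data are paired by design, the plan does not state how the pairing is handled, and an independent-records analysis would overstate the variance of the TV–SP difference. The direction needs only one prediction per model per participant.

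The size depends on assumed event rates, accuracies and agreement. In the cells tabulated, the power lost runs from 6 points (93% against 99%) to 59 points (4% against 63%). PPV and NPV estimates are unaffected and false positives are not inflated, so the cost is power and interval width in one part of Aim 2b. It is worth correcting, but it does not threaten the study.

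**What to change.** In Section 13.2, Aim 2b, replace the reference to logistic regression with: compared by marginal logistic regression (GEE, working independence) clustered on participant, with robust standard errors. A generalised score test for paired predictive values would serve equally. Name one of the two as primary, because they can differ when events are few. If the separate SAP already specifies such a method, cite it here.

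The cost is one sentence, with the same data and standard software. With about 15% events the clustered NPV test is itself somewhat conservative, though less so than the unclustered one.

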Main Exclusionary Criteria	1. Inability to carry out study activities as determined by study staff
Study background and Rationale	At the launch of AT-HOME PD the STEADY-PD III and SURE-PD3 trials were active NINDS-funded phase 3 studies of potential disease-modifying interventions in PD. The long-term observation of participants from these trials, while challenging to implement, was deemed a valuable research opportunity. The reliance on in-person visits and snapshot assessments in a condition characterized by variable symptoms is an important limitation. Tele-visit, web-based surveys, and smartphone-based remote sensor assessments represent particularly promising methods for streamlining study conduct, reducing participant burden, and enabling the collection of data beyond the usual episodic, in-clinic assessments. The objective of this study is to leverage modern technology to develop, pilot and implement a 100% virtual model for long-term follow-up utilizing tele-visit and smartphone platforms for quantitative monitoring of clinician- and patient-reported outcomes (PROs).
Study Platforms and Outcome Measures	
Tele-visit platform – Participants will complete a total of three tele-visits, which will occur at baseline, month 12, and month 24. Some activities will be completed either prior to or post tele-visit by the participant. Assessments will include:
 
 
• Review of reportable events
 
• Review of concomitant medications
 
• MDS-UPDRS parts 1a, 3, and 4 (where applicable)
 
• Montreal Cognitive Assessment (MoCA)
 
• Schwab & England Activities of Daily Living Scale (SEADL)
 
• Clinician Global Impression and Patient Global Impression – Severity and Change
 
• Determination of Falls
 
• Performance of one complete set of active motor and cognitive smartphone application tasks (when applicable)
 
• Review of completion of MDS-UPDRS parts 1b and 2, self-reported falls, and patient global impression – severity and change (with direct link to survey sent ahead of visit)
 
• Review of compliance with smartphone tasks and FI assessments where applicable
 
• Preference and Burden Survey
 

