	
Investigators administering MDS-UPDRS part 3 (motor examination) will be neurologists or nurse practitioners who have obtained formal MDS-UPDRS certification and will have additionally undergone joint training to reconcile scoring differences and minimize inter-rater variability. Tele-visits will be scheduled in either the morning or afternoon according to participant preference and, for participants on symptomatic dopaminergic therapy, the MDS-UPDRS will be preferably performed in the usual ON state.
 
FI web-based survey platform – Participants will be asked to complete a set of standard questionnaires every 3 months through an online observational companion study called FI. Study participants will be encouraged but not required to participate in FI. Standard assessments include:
 
 
• The Parkinson’s Disease Questionnaire, short-form 8 item version (PDQ-8)
 
• MDS-UPDRS part 2
 
• Physical Activity Scale for the Elderly (PASE)
 
• Your Cognition and Daily Activities (PDAQ-15)
 
• Euroqol Five (EQ-5D)
 
• Non-motor symptoms questionnaire (NMS-QUEST)
 
• Geriatric Depression Scale, short form (GDS)
 
• Parkinson’s Disease-Patient Reported Outcomes of Problems (PD-PROP)
 
 
Participants are invited to complete additional PRO surveys about, but not limited to, symptoms, disease progression, quality of life, patient preference or general health.
 
Smartphone session platform (mPower-based app) – We will use mPower 2.0 developed by Sage Bionetworks on both iOS and Android. mPower will include active tasks to be completed (Scientific Aim (SA) 2) and allow passive collection of motor and mobility data with participant permission (for SA3). 14-day smartphone sessions will occur every 3 months. During these sessions, participants will complete smartphone-based motor tasks daily on at least 10 days and cognitive assessments on at least 3 days. Given diurnal variation in active task performance, participants will be asked to select morning or afternoon as their preferred window for completion and to consistently complete the active tasks according to their selected preference.
 
Motor Tasks:
 
 
• Gait task - a 30 second walk
 
• Finger tapping task - 30 seconds of rapid finger tapping in each hand
 

--	---

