Data Management	
Data collected during tele-visits will be entered and maintained in REDCap (a secure web-based survey and data management system). Each participant’s baseline demographic information, concomitant medications, and health history as well as clinical data including PD-PROP from the corresponding SUPER-PD visit, will be transferred from the SUPER-PD REDCap project to the AHPD sub-study REDCap project. All data will ultimately be transferred to Synapse (an open source collaborative platform) for analysis. For any sub-study participants who are participating in the mPower 2.0 component of SUPER-PD, their smartphone data from the corresponding SUPER-PD visit and associated remote 2-week burst will be linked with AT-HOME PD data within Synapse.
 
From Synapse, the cleaned, processed, and event date- and time-transformed dataset will be transferred to the PDBP’s Data Management Resource for further distribution to PDBP investigators and will be made available to the wider research community through their qualified researchers program.

Statistical Analysis	Paired MDS-UPDRS and MoCA scores from in-person and TV assessments of SUPER-PD participants will be pooled with data from SURE-PD3. The accuracy of predicted in-clinic scores based

	
on TV assessments using calibrations from REACT-PD will be summarized by Lin's concordance correlation coefficient, <math>r_c</math>, equivalent to an intra-class correlation (ICC). The REACT-PD calibrations will be judged sufficiently accurate if <math>r_c > 0.8</math>. If we observe insufficient concordance, we will re-calibrate using all available data from REACT-PD, SURE-PD3, and SUPER-PD.

Sample Size	
With a combined sample size of ~60 SURE-PD3 and SUPER-PD participants expected to complete at least one TV close in time to their in-person clinic visit, the study will have 80% power to conclude that the REACT-PD calibrated tele-visit estimates are sufficiently accurate (<math>r_c > 0.8</math> at alpha = 0.05) if the true concordance is at least 0.89.

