## 4. STUDY POPULATION

### 4.1 Participant Numbers

#### 4.1.1 AT-HOME PD Participants

Approximately 420

All individuals with early idiopathic PD enrolled in the STEADY-PD III (NCT02168842) and SURE-PD3 (NCT02642393) studies (N~600) who have consented to be contacted for future research will be asked to participate. We expect approximately 70% of them (N~420) to consent and participate in at least the tele-visit portion of the study. We expect approximately 80% of enrolled individuals (N~340) to participate in the smartphone portion (and thus the smartphone vs tele-visit comparison) of the study. We expect approximately 70% of participants in the smartphone portion (N~240) to consent to passive data collection (and thus contribute to Aim 3). We expect approximately 80% of enrolled individuals (N~340) to participate in the FI portion of the study.

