#### d. Smartphone Sessions (Baseline, Month 3, 6, 9, 12, 15, 18, 21, 24)

- 14-day smartphone sessions will occur on a quarterly basis.
- Given diurnal variation in active task performance, participants will be asked to select morning or afternoon as their preferred window for completion and to consistently attempt to complete the active tasks according to their selected preference.
- Participants will be notified one day before the start of each 14-day session

During these 14-day sessions, participants will be asked to complete daily 4 to 6-minute smartphone-based motor tasks. If they fall behind and are not able to complete at least 10 daily activity sets they can optionally continue for up to 5 additional days.

The following motor activities will be completed by the participant:

- Gait Task
- Finger Tapping Task
- Resting Tremor Task

- Balance task

During these 14-day sessions, participants will be asked to complete an approximately 8-minute set of smartphone-based cognitive assessments on at least 3 of the days.

The following activities will be completed by the participant:

- Digit Span
- Digit Symbol Substitution Tests
- Spatial Working Memory

Participants will be asked to provide basic demographic information through the application once. Participants will also use the application to track their medication adherence relative to tasks and, optionally, self-reported symptoms and triggers. Additionally, participants may perform the active tasks at any time outside of the 14-day smartphone sessions if desired.

Compliance will be actively monitored.

- Participants will receive reminders if they do not perform the activities for two consecutive days and/or after not performing the activities for four days of the 14-day session.
- Participants who enable notifications will receive daily notifications during each 14-day session
- Sage Bionetworks will make quarterly reports available to CHeT/CTCC that will include each participant's compliance status.

e. FI Sessions (Baseline, Month 3, 6, 9, 12, 15, 21, 24)

- AT-HOME PD participants will be asked to complete a set of standard questionnaires through a companion study called FI, (<https://foxinsight.michaeljfox.org>).
- Participants will be asked to complete the questionnaires in the SOA every 90 days. [Refer to SOA] The baseline visit takes approximately one hour to complete; subsequent visits take only 10-15 minutes to complete.

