### 6.3 Fox Insight (FI) Assessments

FI is a separate online research study with a separate consent process. As such, the assessments will not be described in detail. The following validated assessments are included in FI:

- The Parkinson's Disease Questionnaire, short-form 8 item version (PDQ-8)
- MDS-UPDRS part 2
- Physical Activity Scale for the Elderly (PASE)
- Your Cognition and Daily Activities (PDAQ-15)
- Euroqol Five (EQ-5D)
- Non-motor symptoms questionnaire (NMS-QUEST)
- Geriatric Depression Scale, short form (GDS)
- Parkinson's disease-Patient Reported Outcomes of Problems (PD-PROP)

The complete list of assessments can be found in the SOA. Participants are also invited to complete additional PRO surveys about, but not limited to, symptoms, disease progression, quality of life, patient preference and general health.

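### The Aim 2c completion model names no participant-by-platform random effect, so the standard error for tele-visit versus Fox Insight is likely to be too small, by an amount the documents do not fix

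*Combined protocol and SAP*

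**What the plan says.** Section 13.2 (Aim 2c) states that completion rates of patient-reported outcomes on the two platforms "will be compared by mixed effect logistic regression with participant-specific and participant x form random effects (Aim 2c". It does not define a form, which could be the instrument or one platform's version of it. It does not say whether people who never join FI are in the denominator. It gives no significance level for this comparison.

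The two platforms reach participants differently:

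- **Uptake.** The synopsis makes FI voluntary: "Study participants will be encouraged but not required to participate in FI". Section 6.3 adds that "FI is a separate online research study with a separate consent process". Section 4.1.1 first says "We expect approximately 70% of them (N~420) to consent and participate in at least the tele-visit portion of the study", then "We expect approximately 80% of enrolled individuals (N~340) to participate in the FI portion of the study".
- **Schedule.** For tele-visits, the synopsis says "Participants will complete a total of three tele-visits, which will occur at baseline, month 12, and month 24". For FI, Section 5.5 (item e) says "Participants will be asked to complete the questionnaires in the SOA every 90 days".
- **Follow-up.** Under Section 6.1, staff check Parts Ib and II and have gaps filled at the tele-visit. Section 5.5 gives FI automated e-mail reminders at about 45 and 88 days.

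Section 13 leaves further detail to a separate SAP, which takes precedence and is not in the supplied text.

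**The concern.** When the tested factor varies within person, its error term must include how much the effect of that factor varies from person to person. The participant effect is a single propensity common to both platforms. The participant x form effect varies from form to form, and independently across forms. Someone who keeps up with tele-visit surveys but lets FI lapse will miss many FI forms together. The stated effects absorb part of that pattern. The part that is specific to FI and shared across its forms has no term, so the model counts it as repeated evidence about platform.

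Section 3.1 explains that the overlap of surveys was built in to learn whether investigator oversight can improve web-based collection, completion rates included. This model answers that question. If its standard error is too small, the study could report a platform difference, or a precision, that reflects only who happens to use which platform.

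**Working it through.** The plan gives no power, completion rate or variance component for Aim 2c, so there is no stated figure to reproduce. The check is by simulation.

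**Inputs from the documents.** FI participants: 0.80 x 420 = 336, given as about 340. Tele-visit occasions: 3 per form. FI occasions over 24 months: 9, 5 or 3 per form for 3-, 6- and 12-monthly surveys.

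**Assumed, not in the documents.** Two-sided 5% level (0.05 is used in the concordance power statements); conditional logit 1.8 (about 86% completion for a typical participant); participant SD 1.0; participant x form SD 0.7 (for a single instrument, one combined SD of 1.2).

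**Data model.** Logit(completion) = 1.8 + u + (p - 0.5)d + v, where p is 0 for tele-visit and 1 for FI, u is the participant effect, v the participant x form effect, and d the person's own platform difference, with mean zero and SD s. The average platform effect is therefore null. The stated model omits d. It was fitted by maximum likelihood with N = 340 and a Wald test of platform.

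The implied correlation between a person's two platform propensities is (SD_u² - s²/4)/(SD_u² + s²/4). With SD_u = 1.0 it is 0.88, 0.60, 0.28 and 0 at s = 0.5, 1, 1.5 and 2.

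**Layout A:** one shared instrument, form = instrument, 3 tele-visit and 5 FI occasions, 300 replicates.

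| s | Rejection, stated model | Model SE / empirical SD | Rejection with participant x platform added |
|---|---|---|---|
| 0 | 7.3% | 0.111 / 0.114 | 6.0% |
| 0.5 | 5.3% | 0.110 / 0.109 | 4.3% |
| 1 | 9.3% | 0.109 / 0.119 | 6.0% |
| 1.5 | 11.3% | 0.107 / 0.133 | 4.3% |

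**Layout B:** platform-specific forms, 4 tele-visit forms x 3 occasions and 8 FI forms (9, 9, 5, 5, 5, 5, 3, 3), 120 replicates for the stated model. The last column used 100 replicates at s = 0 and 0.5, and 60 at s = 1 and 1.5.

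| s | Rejection, stated model | Model SE / empirical SD | Rejection with participant x platform added |
|---|---|---|---|
| 0 | 7.5% | 0.056 / 0.059 | 5% |
| 0.5 | 9.2% | 0.056 / 0.065 | 7% |
| 1 | 10.0% | 0.058 / 0.070 | 0% |
| 1.5 | 26.7% | 0.060 / 0.105 | 3.3% |
| 2 | 30.8% | 0.063 / 0.119 | not run |

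The standard errors explain the rejections. Expected rejection is 2[1 - Φ(1.96 x SE/SD)]. At s = 1.5 in layout B, 1.96 x 0.060/0.105 = 1.12, which gives 26%. At s = 1, 1.96 x 0.058/0.070 = 1.62, which gives 10%. With the added term at s = 1.5, the model SE rises to 0.102 against an empirical SD of 0.100.

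**Scheduled counts, indexed by correlation.** These runs used 14 tele-visit and 44 FI form-occasions, Part 2 sharing its participant x form effect across platforms, and 200 replicates. The SD of the platform difference is √[2σ²(1 - ρ)], where σ is the total participant SD and ρ the tele-visit/FI correlation.

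| ρ | σ | Difference SD | Rejection, stated model |
|---|---|---|---|
| 1.0 | 1.0 | 0 | 5.0% |
| 0.8 | 1.0 | 0.63 | 10.0% |
| 0.8 | 1.5 | 0.95 | 19.5% |
| 0.5 | 1.0 | 1.0 | 17.0% |
| 0.5 | 1.5 | 1.5 | 29.5% |

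A participant-level paired comparison on the same data rejected in 3.5-5.0%.

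Monte Carlo SEs are about 1.3-1.8 points in layout A, 2.4-4.2 in layout B and 1.5-3.2 in the last set. Near a difference SD of 1, the runs with several forms spread from 10% to about 20%, so the line between modest and larger heterogeneity is not sharp.

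**Non-joiners counted as non-completers.** With N = 420 and 20% having no FI completions, two runs gave a model SE of 0.057 against an empirical SD of 0.156, and 0.059 against 0.167. The variance ratio in the first is (0.156/0.057)² = 7.5. A nominal 95% interval covered 53-54%, taking the estimator's own mean as the target.

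**The case against.** The strongest reply is that the wording does not settle the model. The plan does not say that the participant effect is only an intercept, and it leaves a form undefined. If a form is the platform's own version and a single overlapping instrument is analysed, participant x form is the participant x platform effect, and the simulated error is then about 4-6%. This stands, and it is why the point is conditional. It does not cover the general case: Section 13.2 refers to patient-reported outcomes in the plural, Section 5.5 lists several before each tele-visit, and Section 6.3 lists eight FI instruments.

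Three stronger readings are tempting, and the documents do not support them:

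- **That FI misses are treated as independent.** They are conditionally independent given two random effects, which absorb part of the correlation.
- **That the test is known to reject far too often.** This depends on variances the documents do not give. Staff set-up of FI accounts, compliance review at each tele-visit and FI reminders may bring the two propensities closer together, where inflation is least.
- **That the sevenfold variance shortfall is a false-positive rate.** It arises only if non-joiners are counted, which Section 13.2 does not say. Section 13.5 takes enrolled participants as its base, but for descriptive summaries. In that scenario the platforms do differ.

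It is also fair to say that Aim 2c has no power statement or decision threshold, and that exactly equal completion is an unlikely null. The width of the interval therefore matters more than the error rate.

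**Conclusion.** The point holds in conditional form. Unless a form is platform-specific and one overlapping instrument is analysed, the stated model lacks the error term for a within-participant platform comparison. The direction is consistent across the simulations. Optional FI entry, separate consent and unequal follow-up make within-person platform differences likely.

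The size is a range that rests on the assumed completion rate and variances: close to nominal up to about 10% for modest heterogeneity, about 17-31% for larger heterogeneity with several forms per platform, and about 9-11% for one shared instrument at s of 1 to 1.5. With non-joiners in the denominator, the interval is roughly a third of its proper width (0.057/0.156 = 0.37). This should be corrected, but it affects a secondary feasibility comparison and none of the aims for which the plan gives a power statement.

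**What to change.** In Section 13.2, Aim 2c, and in the separate SAP:

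1. Specify random effects for participant, participant x platform (a random platform slope) and participant x form. Alternatively, keep the stated model and take the platform test and interval from participant-clustered standard errors, by bootstrap or sandwich.
2. Define a form.
3. State whether participants who never join FI are in the denominator. If they are, use the clustered version, because a block of structural zeros is not a normal random effect. The random-slope remedy was not tested in that scenario.

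The cost is a few lines of text and one more variance component, or a resampling step. The interval for the platform difference becomes wider, which is its correct width.
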